10.6.1 Primary Efficacy Analysis

The primary efficacy endpoint of RBC transfusion independence is defined as the absence of any RBC transfusion during any consecutive “rolling” 56 days during the treatment period, ie, Day 1 to 56, Day 2 to 57, Day 3 to 58, etc. Subjects with less than 56 days of assessment during the double-blind treatment period will be counted as non-responders. The primary efficacy analysis will be performed on the ITT population and will compare the RBC transfusion independence rates in the two treatment groups. The number and percentage of subjects achieving RBC transfusion independence and corresponding 95% confidence intervals (CI) will be tabulated and presented by treatment group. A stratified Mantel-Haenszel (MH) chi-squared test, stratifying for average baseline RBC transfusion requirement (≤ 4 units^{§§} versus > 4 units of RBC per 28 days), baseline platelet transfusion status (dependent or independent), country of enrollment (ie, Japan versus ROW) and ECOG performance status (0 to 1 versus 2), at a two-sided alpha level of 0.05, will be used to compare the RBC transfusion independence rate between the two treatment groups. The p-value from the stratified MH chi-square test will be the confirmatory p-value for the test of the null hypothesis that the proportion of subjects achieving RBC transfusion independence is equal between the two treatment groups. Summaries will include the difference in proportions between the two treatment groups with corresponding 95% CI and the common odds ratio with corresponding 95% CI. Subject listings with supporting data will be provided.

The analysis of the primary endpoint will be repeated for the mITT population as the supportive analysis. Additionally, the following sensitivity analyses will be conducted:

- In subjects considered baseline transfusion dependent based on transfusions given for a hemoglobin value ≤ 9.0 g/dL for 56 days;
- In subjects considered baseline transfusion dependent based on transfusions given for a hemoglobin value ≤ 9.0 g/dL for 84 days.

10.6.2 Secondary Efficacy Analyses

10.6.2.1 Key Secondary Efficacy Analyses

Overall survival (OS), defined as the time from randomization to death from any cause, will be calculated using randomization date and date of death, or date of last follow-up for censored subjects. Time to death from any cause is defined as the time between randomization and death from any cause. All subjects will be followed until drop-out, death, or study closure. Drop-out may be due to withdrawal of consent from further data collection or lost to follow-up. Subjects who drop-out or are alive at study closure (or at the time of the interim analysis [Section 10.8]) will have their OS times censored at the time of last contact, as appropriate.

The analysis of OS will be performed using the ITT population for the interim and final analysis. The null hypothesis for testing the key secondary efficacy endpoint, time to death from any cause,

^{§§} As is consistent with medical practice in Japan, 1 unit RBC referenced in this protocol is equivalent to 2 units RBC in Japan.

is that the overall survival distributions for the two treatment groups are equivalent. Overall survival curves will be estimated using Kaplan-Meier (KM) methods and will be compared using a stratified log-rank test, stratifying by average baseline RBC transfusion requirement (≤ 4 units^{§§} versus > 4 units of RBC per 28 days), baseline platelet transfusion status (dependent or independent), country of enrollment (ie, Japan versus ROW) and ECOG performance status (0 to 1 versus 2). The p-value from the stratified log-rank test will be the confirmatory p-value. The p-value from the final analysis of the OS endpoint will be adjusted for the interim analysis in order to preserve the overall alpha level at 0.05 (see [Section 10.8](#) for further details regarding the interim analysis and methods for controlling the overall alpha level). Kaplan-Meier estimates for median OS as well as the 25th and 75th percentiles and associated two-sided 95% CIs will be summarized for each treatment group, unadjusted for the stratification variables. In addition, both the numerical difference and the 95% CI of the difference, in the median, 25th, and 75th percentiles between the two treatment groups will be presented for the un-stratified analysis. Plots of the KM survival curves will be presented for the two treatment groups, without adjustment for the stratification variables.

At the time of the final OS analysis, a stratified Cox proportional hazards model will be used to estimate the corresponding hazard ratio and 95% CI for azacitidine relative to placebo. Additionally, KM methods will be used to estimate the 1-year and 2-year survival probabilities for time to death from any cause. Estimates of the 1-year (365 days) and 2-year (730 days) survival probabilities and corresponding 95% confidence intervals will be presented by treatment group. Median follow-up time, by treatment, will be estimated using KM methods. The analysis of the OS endpoint will be repeated for the mITT-population as a supportive analysis.

In order to assess the potentially confounding effects of other cancer therapy received subsequent to the protocol therapy on the survival estimates, a sensitivity analysis based on the ITT population, will be performed using modified censored criteria. For this analysis, subjects who received subsequent therapy for MDS following discontinuation from their protocol therapy will be censored on the date that the subsequent therapy was started regardless of their survival status at the time of the final analysis. This modified time-to-death endpoint will be analyzed using the same methods as described above for the key secondary efficacy analysis.

The supportive and sensitivity analyses for the OS endpoint will be performed only at the time of the final analysis of OS.

The key secondary study endpoint of OS will be assessed as an interim analysis at the time of the primary analysis and in the final analysis at the time of study closure.

10.6.2.2 Additional Secondary Efficacy Analyses

For secondary efficacy analyses, KM methods will be used to estimate curves for time to event secondary variables. Counts and percentages will be used to describe categorical secondary variables. Secondary efficacy analyses will be performed on the ITT population unless otherwise specified.

Platelet response (HI-P) is defined according to IWG 2006 criteria (Cheson, 2006; Appendix D). HI-P rates will be summarized and compared between the two treatment groups using the same methods as the primary endpoint (see Section 10.6.1).

RBC transfusion independence for 84 days is defined as the absence of any RBC transfusion during any consecutive “rolling” 84 days during the treatment period, ie, Day 1 to 84, Day 2 to 85, Days 3 to 86, etc. Frequency cross-tabulations of RBC transfusion dependency status for 84 days at baseline versus on-treatment will be presented by treatment group.

Duration of RBC transfusion independence for 56 days will be determined only for subjects who achieve RBC transfusion independence on treatment. Duration of RBC transfusion independence is defined as the time from the date transfusion independence is first observed (day 1 of 56 or more days without a transfusion) until the date the subject has a subsequently documented transfusion of RBC. Subjects who maintain RBC transfusion independence through the end of the treatment period will be censored at the date of treatment discontinuation or death, whichever occurs first. Duration of RBC transfusion independence curves will be estimated using KM methods and treatment groups will be compared using a log-rank test.

Time to RBC transfusion independence for 56 days is defined as the time between randomization and the date onset of transfusion independence is first observed (ie, Day 1 of 56 without any RBC transfusions). Subjects who do not achieve RBC transfusion independence during the treatment period will be censored at the date of treatment discontinuation or death, whichever occurs first. Time to RBC transfusion independence curves will be estimated using KM methods and treatment groups will be compared using a log-rank test. A Cox proportional hazards model will be used to estimate the corresponding hazard ratio and 95% CI.

Duration of RBC transfusion independence for 84 days will be determined only for subjects who achieve RBC transfusion independence on treatment. Duration of RBC transfusion independence is defined as the time from the date transfusion independence is first observed (day 1 of 84 or more days without a transfusion) until the date the subject has a subsequently documented transfusion of RBC. Subjects who maintain RBC transfusion independence through the end of the treatment period will be censored at the date of treatment discontinuation or death, whichever occurs first. Duration of RBC transfusion independence curves will be estimated using KM methods and treatment groups will be compared using a log-rank test.

Time to RBC transfusion independence for 84 days is defined as the time between randomization and the date onset of transfusion independence is first observed (ie, Day 1 of 84 without any RBC transfusions). Subjects who do not achieve RBC transfusion independence during the treatment period will be censored at the date of treatment discontinuation or death, whichever occurs first. Time to RBC transfusion independence curves will be estimated using KM methods and treatment groups will be compared using a log-rank test. A Cox proportional hazards model will be used to estimate the corresponding hazard ratio and 95% CI.

Progression to AML is defined as bone marrow blast count $\geq 20\%$. Number and percentage of subjects progressing to AML will be presented by treatment group.

Time to AML Progression is defined as the time from the date of randomization until the date the subject has documented progression to AML. Subjects who do not progress to AML will be censored at the date of last follow-up or at date of death. Time to AML progression curves will be estimated using KM methods and treatment groups will be compared using a log-rank test. KM estimates for median time to AML progression and the 1-year and 2-year AML progression rate will be summarized for each treatment group. A Cox proportional hazards model will be used to estimate the corresponding hazard ratio and 95% CI. [REDACTED]

Erythroid response (HI-E) is defined according to IWG 2006 criteria ([Cheson, 2006](#); [Appendix D](#)). HI-E response will be presented descriptively, by treatment group, using counts and percents.

Duration of RBC transfusion reduction. A subject will be considered as a RBC transfusion reduction responder if the subject had at least 4 units reduction in transfusion units over a consecutive 56 days period compared to the baseline transfusion units in 56 days. The duration of response will be determined for RBC transfusion reduction responders. Subjects who maintain the response through the end of the treatment period will be censored at the date of treatment discontinuation or death, whichever occurs first. Duration of RBC transfusion reduction response will be analyzed descriptively using KM methods.

Platelet transfusion independence is defined as the absence of any platelet transfusion during any consecutive “rolling” 56 days during the treatment period, ie, Day 1 to 56, Day 2 to 57, Days 3 to 58, etc. Subjects will be considered platelet transfusion dependent at baseline if they have received ≥ 2 platelet transfusions during the 56 days immediately preceding randomization and had no consecutive 28-day period during which no platelet transfusions were administered. Frequency cross-tabulations of platelet transfusion status (dependent or independent) at baseline versus on-treatment will be presented by treatment group.

Duration of platelet transfusion independence will be determined only for subjects who are platelet transfusion dependent at baseline and achieve platelet transfusion independence on treatment. Duration of platelet transfusion independence is defined as the time from the date transfusion independence is first documented (day 1 of 56 or more days without a transfusion) until the date the subject has a subsequently documented transfusion of platelets. Subjects who maintain platelet transfusion independence through the end of the treatment period will be censored at the date of treatment discontinuation or death, whichever occurs first. Duration of platelet transfusion independence will be analyzed descriptively using KM methods.

Time to platelet transfusion independence is defined as the time between randomization and the first documented date of onset of transfusion independence (ie, Day 1 of 56 without any platelet transfusions). Subjects who were platelet transfusion dependent at baseline and who do not achieve platelet transfusion independence during the treatment period will be censored at the date of treatment discontinuation or death, whichever occurs first. Subjects who are platelet transfusion independent at baseline will be excluded from the analysis. Time to platelet transfusion independence will be analyzed descriptively using KM methods.

Hematologic response (Complete Remission [CR], Partial Remission [PR], Marrow CR [mCR], Stable Disease [SD], Failure, Relapse after CR or PR, and Cytogenetic Response) is defined according to IWG 2006 criteria (Cheson, 2006; Appendix D). Subjects will be classified according to their best response achieved during treatment for the response categories of CR, PR, mCR, SD, and failure. Only subjects who achieve CR or PR will be included in the Relapse after CR or PR category. Subjects will be evaluated for cytogenetic response regardless of their response status in other categories. For cytogenetic response, subjects will be classified as having a complete or partial response based on the best response achieved during treatment. Hematologic response will be presented descriptively, by treatment group, using counts and percents.

Clinically significant bleeding event is defined as: any intracranial or retroperitoneal bleed; bleeding requiring transfusions of > 2 units of blood/blood products; bleeding associated with a decrease in hemoglobin of > 2 g/dL; or bleeding from any site requiring transfusions of > 2 units of blood. Number and percentage of subjects experiencing a clinically significant bleeding event will be presented by treatment group. Additionally, the number and percentage of subjects by the number of clinically significant bleeding events experienced during the treatment period will be summarized by treatment group.

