6.7 Efficacy

6.7.1 Transfusion Assessment

The type, number of units, reason and date of transfusions are to be collected after the date of randomization and until 28 days after the last dose of IP or until the last study visit, whichever

occurs later. The Hgb value for which any RBC transfusion is given, and the platelet value for which any platelet transfusion is given, must also be recorded on the CRF. Red blood cell and/or platelet transfusions administered for elective surgery will not count toward baseline requirement, efficacy assessment, or progressive disease status.

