9.1 Permitted Concomitant Medications and Procedures

Best supportive care may be used in combination with study therapy if deemed necessary. Best supportive care in both treatment arms for this study includes, but is not limited to, treatment with RBC or whole blood transfusions, fresh frozen plasma transfusions, single donor or pooled donor platelet transfusions, antibiotic, antiviral and/or antifungal therapy, nutritional support as needed, and granulocyte colony stimulating factors for subjects experiencing neutropenic fever/infections. The use of granulocyte colony stimulating factors is also allowed for secondary prophylaxis under certain conditions as described further below. The use of these products will be considered as concomitant treatment and documented as concomitant medications, therapies or procedures. Additional details on the permitted treatments are detailed below.

Subjects who are currently using iron-chelating agents should be on a stable or decreasing dose for at least 8 weeks (56 days) prior to randomization.

Blood product support (RBCs and platelets) may be administered according to institutional standards. Consider platelet transfusion if platelet counts are $< 25 \times 10^9/L$. If appropriate administration of platelets does not correct the platelet counts, contact the Medical Monitors to consider IP dosing delay. The use of these products will be considered as concomitant treatment, and should be collected on the appropriate CRF.

Subjects may be administered supportive and palliative care (eg, pain control) as clinically indicated throughout the study.

Nausea and vomiting are commonly reported adverse reactions associated with azacitidine treatment and subjects may be pre-medicated for nausea and vomiting prior to IP administration at the investigator's discretion. Serotonin (5-HT₃) receptor antagonists (eg, ondansetron) or other antiemetics may be administered approximately 30 minutes prior to IP administration. Additional doses of serotonin (5-HT₃) receptor antagonists or other antiemetics may be administered if required. Pre-treatment or post-treatment with antiemetic medication will be considered as concomitant treatment and should be recorded on the appropriate CRF.

Treatment with antidiarrheal medications is recommended at the first sign of diarrhea as per the guidelines in [Appendix H](#). Pre-medication with antidiarrheal medication for subsequent doses of

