10.2.16. Clinically significant bleeding event

Clinically significant bleeding event is defined as: any intracranial or retroperitoneal bleed; bleeding requiring transfusions of > 2 units of blood/blood products; bleeding associated with a decrease in hemoglobin of > 2 g/dL; or bleeding from any site requiring transfusions of > 2 units of blood. Number and percentage of subjects experiencing a clinically significant bleeding event will be presented by treatment group. Additionally, the number and percentage of subjects by the number of clinically significant bleeding events experienced during the treatment period will be summarized by treatment group.

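### The clinically significant bleeding definition has no fatal-bleed criterion, its fourth criterion repeats its second, and its hemoglobin criterion has no reference value, time window or transfusion rule

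*Protocol*

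**What the plan says.** The proportion of subjects with a clinically significant bleeding event is a named secondary endpoint (protocol 3.2, SAP 4.2). Protocol 10.6.2.2 defines the event by four alternatives:

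1. "any intracranial or retroperitoneal bleed"
2. and 3. "bleeding requiring transfusions of > 2 units of blood/blood products; bleeding associated with a decrease in hemoglobin of > 2 g/dL"
4. "bleeding from any site requiring transfusions of > 2 units of blood"

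SAP 10.2.16 carries the same list forward unchanged. It opens "Clinically significant bleeding event is defined as: any intracranial or retroperitoneal bleed" and ends "bleeding associated with a decrease in hemoglobin of > 2 g/dL; or bleeding from any site requiring transfusions of > 2 units of blood".

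The analysis is a count and percentage by arm, plus a tabulation by number of events per subject. There is no test, and SAP 10.2 limits alpha control to the primary endpoint and overall survival.

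The data behind the definition are collected. Protocol 6.7.2 has every bleeding event recorded on the CRF. For transfusions, protocol 6.7.1 states: "The type, number of units, reason and date of transfusions are to be collected".

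**The concern.** The endpoint is meant to capture serious bleeding in subjects who enter with platelets at or below 75 x 10^9/L. Two features of the definition work against that.

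- **No fatal criterion.** A death from bleeding does not qualify by itself. It must also meet a site, unit or hemoglobin test.
- **Unanchored hemoglobin criterion.** It does not say from which value the fall is measured, over what time, or how intervening transfusions are treated. Subjects enter needing at least 2 RBC units per 28 days (protocol 4.1.1), so hemoglobin declines between transfusions without bleeding. A minor bleed during such a decline could be counted as significant.

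At stake is the face validity and reproducibility of one secondary endpoint: a serious bleed could be left out and some trivial ones included.

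**Working it through.** The plan states no expected bleeding rate and no power for this endpoint, so there is no figure to reproduce.

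**Step 1: does the fourth criterion add anything?** Let b be units of blood and p units of other blood products.

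- Criterion 2: b + p > 2, with no site restriction.
- Criterion 4: b > 2, any site.

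Since p cannot be negative, b > 2 implies b + p > 2. Checking every combination of b and p from 0 to 7 (8 x 8 = 64), criterion 4 adds 0 cases beyond criterion 2. Four listed criteria are three working ones.

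**Step 2: which fatal bleeds fall outside?** A fatal bleed is not counted when all three of these hold:

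- it is neither intracranial nor retroperitoneal;
- two units or fewer were given;
- no hemoglobin fall above 2 g/dL was measured.

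A gastrointestinal or pulmonary bleed that kills before a third unit or a second hemoglobin value fits this description. The documents do not say how often this would happen.

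**Step 3: how large is the fall without bleeding?** The documents give no hemoglobin rise per RBC unit; assume 0.7-1.3 g/dL. For a stable subject, fall = units per 28 days x rise per unit x days/28.

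| Requirement | 7 days | 14 days | 28 days |
|---|---|---|---|
| 2 units per 28 days (entry minimum) | 0.35-0.65 | 0.7-1.3 | 1.4-2.6 |
| 4 units per 28 days | 0.7-1.3 | 1.4-2.6 | 2.8-5.2 |

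These are gross losses in g/dL, and transfusions within the interval offset them. At steady state the fall seen between two transfusions is units per episode x rise per unit: 0.7-1.3 for one unit, 1.4-2.6 for two, 2.1-3.9 for three. Passing 2 g/dL without bleeding therefore needs two-unit episodes with more than 1.0 g/dL per unit, or three-unit episodes.

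Scheduled hematology is weekly in Cycles 1-2, every two weeks in Cycles 3-12 and monthly after that (protocol 6.6.5). With no stated window, the values on either side of a bleed can be 14 to 28 days apart. Coincidental qualification is possible for some subjects, depending on the unstated window and the units given per episode.

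**Step 4: comparison with the rest of the SAP.** SAP 8.2 screens baseline hemoglobin for transfusion timing (a 7-day rule, then a 7/3-day rule). SAP Appendix F excludes values within 7 days after a transfusion when deriving response. SAP 10.2.16 has no such rule.

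**Step 5: can an arm difference be derived?** Suppose a fraction m of each arm has a minor bleed, half of these are upgraded in subjects still transfused, and none in transfusion-independent subjects. Falsely significant bleeds = m x 0.5 x (1 - independence rate). Only the independence rates come from the plan (protocol 10.3).

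| m (assumed) | Independence, azacitidine vs placebo | Azacitidine | Placebo | Gap |
|---|---|---|---|---|
| 0.40 | 0.30 vs 0.05 | 14% | 19% | 5 points |
| 0.40 | 0.15 vs 0.05 | 17% | 19% | 2 points |
| 0.20 | 0.30 vs 0.05 | 7% | 9.5% | 2.5 points |
| 0.20 | 0.15 vs 0.05 | 8.5% | 9.5% | 1 point |

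Now let the upgraded fraction vary freely by arm, with m = 0.20 and 108 subjects per arm. At 30% vs 50%, the counts are 108 x 0.20 x 0.30 = 6.5 against 108 x 0.20 x 0.50 = 10.8, a gap of 4 points. Swapping the fractions reverses the gap, and equal fractions give none. The result follows the assumptions, not the documents.

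**The case against.** The strongest reply is that little depends on this endpoint and the gaps are covered elsewhere. Much of that stands.

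- **Fatal bleeds are reported.** Adverse events leading to death and a listing of all deaths (protocol 10.7), hemorrhagic events as an event category of special interest with its fatal cases tabulated (SAP 11.1.2), and cause of death (SAP 11.2) would all show them. A reader might infer that the trial misses bleeding deaths. It does not; such a death can be lost only from this endpoint.
- **Every criterion requires a bleed.** A routine fall alone is not an event. A reader might infer that every transfusion-dependent subject meets the hemoglobin criterion without bleeding. At the entry minimum, with 0.7-1.0 g/dL per unit, the fall over a full 28 days is 1.4-2.0 g/dL and never exceeds 2.
- **Direction of bias.** A reader might infer that minor bleeds are upgraded more often on placebo, favouring azacitidine. The Step 5 model gives that sign only because it assigns transfusion-independent subjects no false events. A responder needs just one 56-day transfusion-free window (protocol 10.6.1) and may be transfused before and after it. Thrombocytopenia is also a listed risk of the drug (protocol 1.4.1). Blinding does not remove a difference that arises from hemoglobin trajectories, but neither does the plan show that one exists.
- **Pooled platelets.** Protocol 9.1 allows "single donor or pooled donor platelet transfusions", and a reader might infer that one pooled dose passes the unit threshold. The documents do not say how a pool is entered on the CRF, so this is unsupported. Requiring that the units be given for the bleed is already the sense of the second criterion.

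The missing fatal criterion, the redundancy and the unanchored hemoglobin criterion remain.

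**Conclusion.** The point holds in limited form. Two defects are certain from the text: the fourth criterion contributes nothing, and a fatal bleed meeting the three conditions in Step 2 is classed as not clinically significant. A third is an omission: without a reference value, window or transfusion rule, some minor bleeds may be counted because they coincide with decline between transfusions. How many depends on the assumed rise per unit, the units per episode and the interval between values. The size and direction of any difference between arms cannot be determined from the documents. The endpoint is descriptive and outside alpha control, so primary and overall survival inference are unaffected.

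**What to change.** 1. Replace the redundant fourth criterion with any bleeding with a fatal outcome (Grade 5).
2. For the hemoglobin criterion, state the pre-bleed reference value, a window compatible with the visit schedule, and transfusion handling in line with SAP 8.2 and Appendix F. A window as short as 7 days would often lack paired values once hematology is every two weeks or monthly.
3. Tabulate events by the criterion that qualified them.

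The Amendment 6.0 rationale says the primary analysis report was final as of 04-Feb-2020, and SAP 10 has this endpoint analysed once, with the primary. The prespecified count should therefore stay as the main result. Present the corrected definition as a labelled supplementary derivation, with the rules fixed and applied blind to arm.

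The cost is a small re-derivation from bleeding, transfusion, laboratory and death data already collected, and counts that differ slightly from those reported.
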